12.3 Assessment of Effectiveness

12.3.1 Statistical Analysis

12.3.1.1 Descriptive Statistics

In general, data will be summarized by treatment group and visit as appropriate. Data will be summarized separately at the subject and eye levels. Subject level summaries will summarize the average of the subject's 2 eyes for continuous variables and the worst case over both eyes for categorical variables.

Summaries for continuous variables will include the sample size, mean, standard deviation, median, minimum, and maximum. Means and medians will be presented with one more decimal place than the recorded raw data. Standard deviations will be presented with 2 more decimal places than the recorded raw data. Minima and maxima will be presented with the same number of decimal places as the recorded raw data. Values with magnitude less than 1 will be presented with a leading zero to the left of the decimal (eg, 0.123 or -0.123).

Categorical data will be summarized using frequencies and percentages. Percentages will be presented with one decimal place. Percentages may not be presented when the count is zero. Unless otherwise specified the denominator for percentages will be the number of non-missing values within the group being presented.

12.3.2 Primary Effectiveness Analysis

At the 1-Week Follow-up Visit, subjects with non-missing logMAR acuities 0.04 or better in both eyes will be classified as “0.04 or Better.” Subjects with at least one logMAR acuity > 0.04 at the visit will be classified as “Worse than 0.04.” Subjects with at least one missing value at the visit will not be classified and their classification value will be assigned as missing. Visual acuity of 0.04 logMAR is the acuity where an individual subject would be given credit for reading logMAR 0.0 and logMAR 0.0 is equivalent to Chinese logarithmic visual acuity chart value of 5.0.

The summaries and analyses of the primary effectiveness endpoint will be at the subject level.

Use of the ITT Population and imputation of missing values are not conservative practices in non-inferiority analyses. Consequently, the PP Population will be used for the primary analysis without imputation of missing data.

Primary Non-Inferiority Analysis with the Per Protocol Population

VA Effectiveness will be summarized categorically (0.04 or Better, Worse than 0.04) by treatment group at the 1-Week Follow-up Visit for the Per Protocol (PP) Population in a table. Missing data will not be imputed for this primary analysis of the PP Population. The denominator for percentages will be the number of non-missing values.

The difference between treatment groups (Test minus Control) in the proportion of subjects classified as “0.04 or Better” will be estimated. An asymptotic Wald non-inferiority test (without continuity correction; using the sample variance; alpha risk = 0.025) and the associated two-sided 95% confidence interval will be used to test the statistical hypothesis. The difference between treatment groups (in percentage units), the asymptotic standard error for the difference (in percentage units), the associated Z value, the p-value for the non-inferiority test, and a two-sided 95% confidence interval (in percentage units) around the difference will be presented. [REDACTED]

Sensitivity Analysis Using the ITT Population

VA Effectiveness will be summarized categorically (0.04 or Better, Worse than 0.04) by treatment group at the 1-Week follow-up visit for the ITT Population in a table. The denominator for percentages will be the number of non-missing values. Missing data will not be imputed for this categorical summary.

If there are no missing lens VA data at the 1-Week follow-up visit for ITT subjects, then the following will be completed.

- The difference between treatment groups (Test minus Control) in the proportion of subjects classified as “0.04 or Better” will be estimated.

If there are missing lens VA data for ITT subjects at the 1-Week follow-up visit then missing data will be imputed as follows prior to hypothesis testing.

- The difference between treatment groups (Test minus Control) in the proportion of subjects classified as “0.04 or Better” and the asymptotic standard error will be estimated by imputation.
- An estimated difference between treatment groups and two-sided asymptotic Wald 95% confidence interval around the difference will be constructed via combination of the proportion differences and standard errors from the imputations.
- If all of the imputations result in the same estimated difference and confidence interval, then the results of a single imputation may be used.

The estimated difference between treatment groups (Test minus Control) in the percentage of subjects classified as “0.04 or Better” will be presented along with the two-sided asymptotic Wald 95% confidence interval around the difference.

Evaluation of Sensitivity to Missing Data

As an evaluation of sensitivity to missing VA Effectiveness data, a best-case analysis, worst-case analysis, and tipping point analysis will be completed for the ITT Population (Xu et al, 2009). If there are no missing ITT Population data then these analyses will not be completed.

Evaluation of the Influence of Site on the Treatment Effect

VA Effectiveness will be summarized categorically (0.04 or Better, Worse than 0.04) by treatment group and site for the ITT Population in a table. This will be a subject level summary. The denominator for percentages will be the number of non-missing values. Missing data will not be imputed.

A Breslow-Day test for homogeneity of odds ratios will be used to evaluate the consistency of the treatment effect among the sites. If the p-value from this test is less than 0.05 then the difference between sites will be considered to be statistically significant.

Evaluation of the Influences of Age, Sex, and Descent on the Treatment Effect

VA Effectiveness will be summarized categorically (0.04 or Better, Worse than 0.04) by treatment and age group (less than 30, 30 to 39, 40 to 49, 50 or greater) for the ITT Population in a table. The denominator for percentages will be the number of non-missing values. Missing data will not be imputed.

A Breslow-Day test for homogeneity of odds ratios will be used to evaluate the consistency of the treatment effect among the age groups. If the p-value from this test is less than 0.05 then the difference among age groups will be considered to be statistically significant.

VA Effectiveness will be summarized categorically (0.04 or Better, Worse than 0.04) by treatment and sex (Male, Female) for the ITT Population in a table. This will be a subject level summary. The denominator for percentages will be the number of non-missing values. Missing data will not be imputed.

A Breslow-Day test for homogeneity of odds ratios will be used to evaluate the consistency of the treatment effect between the sexes. If the p-value from this test is less than 0.05 then the difference between the sexes will be considered to be statistically significant.

VA Effectiveness will be summarized categorically (0.04 or Better, Worse than 0.04) by treatment and descent (Chinese, Non-Chinese) for the ITT Population in a table. This will be a subject level summary. The denominator for percentages will be the number of non-missing values. Missing data will not be imputed.

A Breslow-Day test for homogeneity of odds ratios will be used to evaluate the consistency of the treatment effect between the descent categories. If the p-value from this test is less

than 0.05 then the difference between the descent categories will be considered to be statistically significant.

VA effectiveness will also be summarized descriptively for each scheduled follow up visit.

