The difference between treatment groups (Test minus Control) in the proportion of subjects classified as “0.04 or Better” will be estimated. An asymptotic Wald non-inferiority test (without continuity correction; using the sample variance; alpha risk = 0.025) and the associated two-sided 95% confidence interval will be used to test the statistical hypothesis. The difference between treatment groups (in percentage units), the asymptotic standard error for the difference (in percentage units), the associated Z value, the p-value for the non-inferiority test, and a two-sided 95% confidence interval (in percentage units) around the difference will be presented. [REDACTED]

[REDACTED]

[REDACTED]

Sample Size Calculations:

Primary Effectiveness Endpoint

The null hypothesis is that the difference in the proportion of subjects with both eyes “0.04 or Better” between the test group (π_T) and the control group (π_C) is less than or equal to the negative value of the non-inferiority margin ($-\delta$). The alternative hypothesis is that the difference in proportions is greater than the negative value of the non-inferiority margin.

$$H_0: \pi_T - \pi_C \leq -\delta$$

$$H_1: \pi_T - \pi_C > -\delta$$

In a previous evaluation of Biotrue ONEday for Astigmatism Soft Contact Lenses, 92.5% of subjects with baseline logMAR BSCVA of 0.04 or better achieved the primary effectiveness endpoint of this study at the follow-up visit. Consequently 92.5% is the expected percentage of subjects “0.04 or Better” in the Test and Control groups. [REDACTED]

A one-sided alpha risk of 0.025 (eg, a two-sided 95% confidence interval) will be used to test the hypothesis.

When the sample size in each group is 109 subjects, a two-group large-sample normal approximation test of proportions with a one-sided 0.025 significance level will have 80% power to reject the null hypothesis that the test is inferior to the control [REDACTED] in favor of the alternative hypothesis that the test lens is non-inferior, assuming that the expected difference in proportions is 0.000 and the proportion in the standard group is 0.923.

Overall Power and Sample Size

In order to allow for dropouts of up to 10%, at least approximately $109/(1-0.1) \approx 122$ subjects will be enrolled in each treatment group for a total enrollment of approximately 244 subjects.

3 Table of Contents

1	TITLE PAGE	1
2	SYNOPSIS	6
3	TABLE OF CONTENTS	12
4	LIST OF ABBREVIATIONS AND DEFINITIONS OF TERMS	16

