9.1 Randomization and Methods of Assigning Subjects to Treatment Groups

Subjects will be randomized to one of 2 treatment arms at a 1:1 ratio, wearing either Test or Control lenses in both eyes for the duration of the study. Randomization will be stratified by site, ancestry (Chinese, Non-Chinese), and sphere power sign (positive, negative).

Subjects will be randomized sequentially.

The randomization scheme will be produced prior to study enrollment by an unmasked statistician not otherwise involved in the trial. An unmasked designee at each site will be responsible for dispensing the study lenses according to the randomized treatment assignments. Lenses will be dispensed directly to the subject by the unmasked designee, thereby maintaining Investigator masking. In an effort to ensure that the Investigator remains masked, the unmasked designee MUST dispense the study lenses and MUST remove foils from their blister packs out of the Investigator's sight immediately prior to dispensing. Unworn (unopened) lenses that are returned by the subject to the site must be returned in a manner so as not to unmask the Investigator and other staff members at the site (ie, returned in an opaque bag or container labeled with subject identifiers). The unmasked designee will be responsible for physically examining the unopened lens blister package labeling to ensure the appropriate lenses were returned, and will document the return of these lenses in the CTM Product Accountability Log. The Investigator should contact the Medical Monitor prior to emergency unmasking of study arm assignment. In an urgent situation, however, where knowledge of the study arm assignment is critical to subject safety, the code may be broken by requesting the allocated treatment for that subject from the unmasked designee.

The Investigator must notify the Sponsor/Medical Monitor and/or Study Manager as soon as possible after emergency unmasking. In addition, the Investigator must record the date, time, and reason for unmasking the study arm assignment in the source documentation.

Study Monitors will become unmasked during site visits as they perform reconciliation activities and/or review randomization assignments, product accountability records, product inventory, and subject records. Study Monitors must take care not to unmask the Study Manager, other Bausch + Lomb staff, Contract Research Organization (CRO) staff, or site staff during the study.

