12.1 Determination of Sample Size

12.1.1 Primary Effectiveness Endpoints

The null hypothesis is that the difference in the proportion of subjects with both eyes "0.04 or Better" between the test group (π_T) and the control group (π_C) is less than or equal to the negative value of the non-inferiority margin ($-\delta$). The alternative hypothesis is that the difference in proportions is greater than the negative value of the non-inferiority margin.

$$H_0: \pi_T - \pi_C \leq -\delta$$

$$H_1: \pi_T - \pi_C > -\delta$$

In a previous evaluation of Biotrue ONEday for Astigmatism Soft Contact Lenses, 92.5% of subjects with baseline logMAR BSCVA of 0.04 or better achieved the primary effectiveness endpoint of this study at the follow-up visit. Consequently 92.5% is the expected percentage of subjects "0.04 or Better" in the Test and Control groups. The non-inferiority margin will be set at 10% and the lower confidence limit will be compared to -10%.

A one-sided alpha risk of 0.025 (eg, a two-sided 95% confidence interval) will be used to test the hypothesis.

When the sample size in each group is 109 subjects, a two-group large-sample normal approximation test of proportions with a one-sided 0.025 significance level will have 80% power to reject the null hypothesis that the test is inferior to the control (the difference in proportions, $\pi_T - \pi_C$, is -0.10 or less) in favor of the alternative hypothesis that the test lens is non-inferior, assuming that the expected difference in proportions is 0.000 and the proportion in the standard group is 0.925.

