12.1.2 Overall Power and Sample Size

In order to allow for dropouts of up to 10%, at least approximately $109/(1-0.1) \approx 122$ subjects will be enrolled in each treatment group for a total enrollment of approximately 244 subjects.

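### The primary Wald test is stated at one-sided 0.025, but at the plan's own inputs its exact error is about 0.028 to 0.031; state this and prespecify a score interval beside it

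*Combined protocol and SAP*

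**What the plan says.** The synopsis and section 12.3.2 specify the same primary test: "An asymptotic Wald non-inferiority test (without continuity correction; using the sample variance; alpha risk = 0.025) and the associated two-sided 95% confidence interval". It is applied to the Per Protocol population without imputation. Using the sample variance means that each arm's observed proportion supplies its own variance, so the test is unpooled.

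Section 12.1.1 sets the error rate: "A one-sided alpha risk of 0.025 (eg, a two-sided 95% confidence interval) will be used to test the hypothesis". It also sets the decision rule: "The non-inferiority margin will be set at 10% and the lower confidence limit will be compared to -10" per cent. The planning rate comes from the Test lens: "In a previous evaluation of Biotrue ONEday for Astigmatism Soft Contact Lenses, 92.5% of subjects with baseline logMAR BSCVA of 0.04 or better" met the endpoint. The same 92.5% is then assumed for Control, for which the documents give no data. Section 12.1.1 derives 109 per arm for 80% power. Section 12.1.2 raises this to 122 per arm: "In order to allow for dropouts of up to 10" per cent.

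In section 9.1, "Randomization will be stratified by site, ancestry (Chinese, Non-Chinese), and sphere power sign (positive, negative"). For the ITT sensitivity analysis with missing data, section 12.3.2 again uses Wald: a "two-sided asymptotic Wald 95% confidence interval around the difference will be constructed via combination" of the imputation results.

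The text directly after the primary test is redacted in both the synopsis and section 12.3.2.

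**The concern.** The unpooled Wald test estimates its standard error from the observed proportions and not from proportions constrained to the null hypothesis. When success rates are near 1 and the arms hold about 100 subjects, its real error can differ from its nominal error. Here the expected rate is 92.5%, and the lower confidence limit alone decides the trial. If that limit errs too often on the favourable side, a lens that is truly 10 points worse passes more often than the stated 2.5%.

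The direction matters because section 12.3.2 chooses the Per Protocol population, without imputation, on the ground that the alternatives are not conservative for non-inferiority. A primary test that leans the other way works against that aim.

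**Working it through.** **Inputs.** Margin 0.10, one-sided 0.025 (critical value 1.96), expected rate 0.925 in both arms and 109 evaluable per arm (section 12.1.1); 122 enrolled per arm (section 12.1.2); unpooled variance (section 12.3.2).

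**The plan's own figure.** n = (1.960 + 0.842)² × 2 × 0.925 × 0.075 / 0.10² = 108.9, so 109 per arm. Then 109 / 0.9 = 121.1, so 122. Both reproduce. The synopsis prints 0.923 instead of 0.925 in its power sentence; at 0.923 the formula gives 112.

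**Exact error of the Wald test.** Let a and b be the observed Test and Control proportions. The test passes when

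a − b − 1.96 × √[a(1−a)/n + b(1−b)/n] > −0.10.

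On the null boundary the true rates are Control 0.925 and Test 0.825. Treat the arms as independent binomials and add the probabilities of all outcome pairs that pass. For comparison, the Farrington-Manning (FM) score test replaces the standard error with one built from the maximum-likelihood proportions restricted to a difference of −0.10.

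| Evaluable per arm | Wald error | FM error | Wald passes, FM fails |
|---|---|---|---|
| 109 | 0.0298 | 0.0252 | 0.46% |
| 122 | 0.0285 | 0.0247 | 0.38% |
| every equal n, 100 to 122 | 0.0279 to 0.0307 | 0.0229 to 0.0252 | 0.37% to 0.69% |

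FM passing while Wald fails has a probability of effectively zero. A simulation of 4 million trials at each size also gives Wald errors of 0.0298 and 0.0285. With Control at 0.923 the Wald errors are 0.0296 and 0.0284.

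**Which tail.** At 109 per arm on the boundary, the lower limit lies above −10% in 2.98% of trials, and the upper limit lies below −10% in 2.35%. The excess is in the deciding limit.

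**What it changes in practice.** Take Control 102/109 and Test 99/109. The difference is −3/109 = −2.75% and the standard error is 3.63%, so the lower limit is −2.75% − 1.96 × 3.63% = −9.86%. Wald passes (p = 0.0229); the score test does not (p = 0.0323) and needs 100/109. For Control counts from 97 to 108 of 109, the score test needs at most one more Test success than Wald.

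**Sensitivity to assumptions.**
- *Unequal arms.* Seven slightly unbalanced splits gave Wald errors from 0.0273 (Test 112, Control 106) to 0.0305 (Test 109, Control 111).
- *Strata.* With two equal strata at assumed Control rates of 87.5% and 97.5% and a 10-point deficit in each, Wald gives 0.0284 at 109 and 0.0271 at 122; FM gives 0.0239 and 0.0234.
- *Control rate.* At 109 per arm and assumed Control rates of 80 / 85 / 90%, Wald gives 0.0261 / 0.0267 / 0.0283. At assumed 95 / 97 / 99%, it gives 0.0327 / 0.0375 / 0.0512.

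**Power when both arms are truly at 92.5%.**

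| Evaluable per arm | Wald | FM |
|---|---|---|
| 109 | 80.3% | 75.5% |
| 111 | 81.0% | 75.0% |
| 115 | 81.4% | 77.8% |
| 120 | 84.4% | 79.0% |
| 122 | 84.0% | 80.4% |

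FM power is below 80% at every equal n from 100 to 121 (79.5% at 121).

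**The case against.** The plan calls the test asymptotic and sizes the trial with a large-sample approximation, so 0.025 can be read as a nominal level, and the analysis matches the sample-size method. The excess is also small: at 109 per arm and Control 92.5%, Wald error equals 0.025 when the true deficit is 10.34 points, so the trial behaves as if its margin were 10.34 and not 10. Differences between strata shrink the excess further. Replacing Wald costs more than it saves at the planning assumptions: at 109 per arm it removes 0.46% of trials at the boundary but loses 4.8 percentage points of power (80.3% to 75.5%), about ten times as much. A score-based primary would also differ in method from the Wald ITT sensitivity interval.

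Most of this stands. It is a good reason not to insist on a new primary test. It does not remove the point: section 12.1.1 attaches a specific error rate to the deciding test, and at the plan's own inputs the test exceeds that rate at every equal arm size from 100 to 122.

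Three stronger readings are tempting, and the documents do not support them:
- *The plan contains no score or exact check.* The redaction directly after the primary test means this cannot be known.
- *The error is 3.3 to 5.1%.* Those figures need Control rates of 95 to 99%, which are assumptions, as are the lower rates that reduce the excess.
- *The sample size is wrong.* It reproduces for the Wald test.

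**Conclusion.** The point holds as a modest mismatch between the stated error rate and the one delivered. At Control 92.5% and a 10-point margin, the one-sided error is 0.0298 at 109 per arm, about half a percentage point or one fifth above 0.025 (0.0298 / 0.025 = 1.19), and 0.0285 at 122. The excess favours the non-inferiority claim. It matters only if the result is borderline, typically by one Test success.

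These figures rest on independent binomial outcomes, equal arms and the planning rate. They do not model the stratified randomisation. They do not depend on what the redacted text says about supportive analyses, because the readable text makes the Wald lower limit the deciding quantity. They do not show that Wald must be abandoned.

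**What to change.** Before unmasking, amend section 12.3.2 and the synopsis as follows:
1. Keep the Wald test and interval as the primary analysis, and state that the actual one-sided error at the planning rates is about 0.028 to 0.031 (equal arms of 100 to 122).
2. Prespecify the Farrington-Manning score test and its matching 95% interval against −10% on the Per Protocol population, reported beside Wald.
3. State that non-inferiority shown by Wald but not by the score interval will be described as not robust.

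If the redacted text already contains such a check, only the statement of the actual error and the rule for discordant results may need adding.

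The cost is one extra standard analysis and a slightly less favourable stated error. Enrolment and the power of the primary test do not change, and the Per Protocol and ITT intervals remain comparable in method.

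If the sponsor wants the primary test to hold 0.025 more closely, it can make the score test primary. FM is itself asymptotic (0.0252 at 109). Section 12.1.1 would then have to restate power: about 75.5% at 109 evaluable per arm, below 80% at every equal n up to 121, and 80.4% only if all 122 per arm are evaluable.

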8.2 Subject Inclusion Criteria

To be eligible for entry into the study, the subject must meet the following inclusion criteria:

1. Subject must be of legal age (at least 18 or as defined by state law) on the date the ICF is signed and have the capacity to provide voluntary informed consent.
2. Subject must be able to read, understand and provide written informed consent on the IRB approved ICF and provide authorization as appropriate for local privacy regulations.
3. Subject must have physiologically normal anterior segments not exhibiting clinically significant biomicroscopy findings (greater than Grade 1 and/or presence of infiltrates) and have clear central 6 mm corneas.
4. Subject must be an adapted wearer of soft contact lenses, wear a lens in each eye, and each lens must be of the same manufacture and brand.
5. Subject must have vision correctable through spherocylindrical refraction to 45 letters (0.04 logMAR) or better (distance, high contrast) in each eye. Visual acuity of 0.04 logMAR is the acuity where an individual subject would be given credit for reading logMAR 0.0 and logMAR 0.0 is equivalent to Chinese logarithmic visual acuity chart value of 5.0.
6. Subject must be myopic or hyperopic and require lens correction from +4.00 diopter (D) to -9.00 D in both eyes.
7. Subject must be a habitual wearer of toric soft contact lenses.
8. Subject must be able to be fit in both the Test and Control lenses in the listed parameters.
9. Subject have no active ocular disease or allergic conjunctivitis.
10. Subject must not be using any topical ocular medications.
11. Subject must agree to wear their study lenses on a daily wear basis for the duration of the study.
12. Subject must be willing and able to follow the visit schedule and follow instructions for use of the study products.

Written informed consent, enrollment in the study, or dispensing of study products cannot begin until the Investigator has received IRB approval to conduct the study. The Sponsor and IRB must approve any advertising used to recruit subjects prior to use of that advertising.

All consented subjects must be accounted for, whether they participate in the study or not. Bausch + Lomb will provide a Screening Log on which to enter information for each subject

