11.1 Visit Schedule

11.1.1 Screening Visit

A Screening Log will be provided by the Sponsor to track all consented subjects that the Investigator interviews regarding the study. Once all available lines on the Screening Log have been completed, or the Investigator has fulfilled his/her quota of subjects, the Investigator will sign and date the form to verify that all the subjects who interviewed for the study have provided informed consent and Health Insurance Portability Accountability Act (HIPAA) authorization. The Investigator will send the bottom copy of each Screening Log to the Sponsor as soon as the quota of subjects for his/her site has been enrolled into the study. The Investigator will retain the original document for their records.

After obtaining written informed consent, prospective subjects will be screened to determine whether they meet the entry criteria for the study.

Screening will proceed as follows:

- a. Enter the subject information on the next available line of the Screening Log.
- b. Collect the following lens history information from the subject: average daily wearing time hours lenses worn on the day of this visit current lens brand and lens wear modality, current lens care products. Collect the relevant medical history for the past 2 years.
- c. Collect demographic and baseline information and perform the following baseline/Screening assessments (without lenses) and record in the subject's source document: uncorrected distance VA, autorefraction, spherocylindrical refraction, distance best spectacle-corrected visual acuity (BSCVA), keratometry, intraocular pressure (IOP) using the TonoPen or the Goldmann Applanation Tonometer, dilated fundus exam, direct ophthalmoscope exam (non-dilated).
- d. Perform a slit lamp examination (remove the lenses if the subject wore lenses to the visit). Record and diagram the results and findings in the subject's source document and appropriate eCRF:
 - any ungraded finding marked as "PRESENT"
 - any new corneal scars
 - any neovascularization within the central 6 mm of the cornea
 - any corneal staining
 - any corneal infiltrate (record details on the Corneal Infiltrates Evaluation Form [\[Appendix E\]](#))
 - any other graded slit lamp findings Grade 2 or greater
- e. If the subject is eligible, collect AE and Symptoms/Complaints information from the subject regarding their habitual lenses.

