- f. Assign subject numbers to each eligible subject in ascending order. A log will be provided to each site to maintain a record of the subject numbers assigned to each enrolled subject. Record the assigned subject ID on the Screening Log.
- g. The unmasked designee will determine the eligible subject's randomized lens type (treatment group).
- h. The Screening Visit eCRF should be completed only if the subject is a "Screen Pass."
 - i. Conduct a diagnostic fitting evaluation for the Test or Control lenses to the lens the subject is randomized to, using the Fitting Sets provided. The prescription determined from this fitting assessment will be used to dispense/order Test or Control lenses according to the lens the subject is randomized to. The Investigator should ensure that the lens was inserted with the toric etch marks roughly at the 6 o'clock positions and /or allow the trial lenses to properly settle on the eye for a minimum of 5 minutes. Collect the following information for both study lenses using the study site's standard diagnostic fitting techniques:
 - Collect Symptoms/Complaints information using the Symptoms/Complaints Rating Scales in [Appendix A](#)
 - lens wettability
 - lens centration
 - lens movement
 - lens rotation
 - lens deposits

Record the lens parameters to be dispensed/ordered based on the diagnostic fitting.

- j. "Screen Fail" subjects are ineligible and non-dispensed and cannot be enrolled in the study if parameters are unavailable or fit is deemed unacceptable. The reason for screen failure must be documented and maintained with a copy of their ICF.
- k. Indicate on the Screening Log whether the subject is a "Screen Pass" or "Screen Fail." "Screen Fail" subjects are ineligible and cannot be randomized in the study. The reason for screen failure must be documented on the Screening Log and in the subject record, and maintained with a copy of their ICF.

Only "Screen Pass" subjects should be randomized in the study.

- l. Re-emphasize the exclusion criterion stating that if the subject is a female of child bearing potential and is pregnant and or breast feeding, she is ineligible to be a part of the study.

For each subject, use the Material Order Form for Study 885 to order the appropriate study contact lenses (test or control). Schedule the subject for their Dispensing Visit within 3 weeks as instructed by the Sponsor.

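### The visible primary test makes no use of screening BSCVA; prespecifying an adjusted risk difference is an optional, cheap gain in efficiency, not the correction of an error

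*Combined protocol and SAP*

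**What the plan says.** Section 12.3.2 estimates Test minus Control in the proportion of subjects with both eyes at 0.04 logMAR or better at one week. It uses the Per Protocol Population without imputation and applies "An asymptotic Wald non-inferiority test (without continuity correction; using the sample variance; alpha risk = 0.025" with the matching two-sided 95% interval. Section 12.1.1 sets the margin at 10 points. No covariate or stratum is named. The text directly after this description is blacked out, here and in the synopsis.

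Three other places bear on the point:

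- **BSCVA at entry.** Criterion 5 of section 8.2 reads "Subject must have vision correctable through spherocylindrical refraction to 45 letters (0.04 logMAR) or better (distance, high contrast) in each eye". Screening step c in section 11.1.1 records "distance best spectacle-corrected visual acuity (BSCVA". Assignment comes later, at step g: "The unmasked designee will determine the eligible subject's randomized lens type (treatment group".
- **Planning rate.** Section 12.1.1 takes its expected rate from an earlier evaluation in which "92.5% of subjects with baseline logMAR BSCVA of 0.04 or better achieved the primary effectiveness endpoint".
- **Strata.** Section 9.1 says "Randomization will be stratified by site, ancestry (Chinese, Non-Chinese), and sphere power sign (positive, negative". Site and descent return in 12.3.2 only as tables and homogeneity tests ("A Breslow-Day test for homogeneity of odds ratios will be used to evaluate the consistency of the treatment effect among the sites", and likewise a test that "will be used to evaluate the consistency of the treatment effect between the descent categories"). Those tests do not adjust the estimate. Sphere sign appears in no visible analysis in section 12.

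**The concern.** Screening BSCVA is a pre-assignment measurement of nearly the same quantity as the endpoint. It is required of every eligible subject and costs nothing more to use. If it predicts which subjects reach 0.04 in their study lenses, adjusting for it removes outcome variance that the crude test leaves in, and the lower limit moves up slightly on average when the lenses are equivalent. At stake is a little precision in a trial planned at 80% power. Timing also matters: an adjusted result carries weight only if it is specified before unmasking.

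**Working it through.** **1. The plan's own figure.** Inputs from section 12.1.1: p = 0.925 in both groups, margin 0.10, one-sided alpha 0.025, power 80%.

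- n = (1.960 + 0.842)² × 2 × 0.925 × 0.075 / 0.10² = 108.9, so 109 per group.
- SE at 109 = √(2 × 0.925 × 0.075 / 109) = 0.0357. The 95% half-width is 1.96 × 3.57 = 6.99 points.
- Power = Φ(0.10/0.0357 − 1.96) = 80.0%. Exact binomial enumeration of the Wald rule gives 80.3%.
- 109/0.9 gives 122 per group, 244 in total.

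All stated figures reproduce. (One synopsis sentence prints 0.923, which would give 112; that is a separate inconsistency.)

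**2. What adjustment could buy.** If the covariate explains a share R² of outcome variance, the variance is multiplied by (1 − R²), and power = Φ(0.10/(0.0357√(1 − R²)) − 1.96):

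| R² | 0 | 0.02 | 0.05 | 0.10 |
|---|---|---|---|---|
| Power at 109 per group | 80.0% | 80.8% | 82.0% | 84.0% |

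At R² = 0.05 the half-width falls from 6.99 to 6.99 × √0.95 = 6.81 points.

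**3. What it could cost.** With k useless covariates, the variance grows by roughly (218 − 2)/(218 − 2 − k). The power change is −0.2 points for k = 1, −0.6 for k = 3 and −2.9 for k = 15 (BSCVA, ancestry, sphere sign and 12 site terms).

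**4. Simulation.** Change in power against the crude test, in points, for a linear model with a robust variance, by assumed odds ratio (OR) per SD of BSCVA:

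| Model, variance, trials per scenario | OR 1 | 1.5 | 2 | 3 | 4 |
|---|---|---|---|---|---|
| BSCVA, HC1, 6,000 | −0.2 | 0.0 | −0.1 | +1.3 | +1.9 |
| BSCVA, HC0, 20,000, simple allocation | −0.1 | +0.1 | +0.5 | – | +2.3 |
| BSCVA, HC3, 20,000, simple allocation | −0.7 | −0.6 | −0.2 | – | +1.6 |
| BSCVA, HC3, 20,000, stratified blocks | −0.7 | −0.2 | +0.6 | +1.2 | +2.0 |
| BSCVA, ancestry and sphere sign, HC3, 20,000, stratified blocks | −1.1 | −0.6 | +0.2 | +0.7 | +1.6 |

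The 20,000-trial runs assume normal BSCVA, mean −0.04 and SD 0.06, cut at 0.04 as criterion 5 requires. The stratified runs also assume 13 equal sites, blocks of 4, half Chinese ancestry and 10% plus-power subjects. Most of the loss at OR 1 comes from HC3 and the added terms. Ancestry and sphere sign alone changed power by −0.7 to 0.0 points, even when prognostic. Twelve site terms cost a further 2.0 to 2.1 points if site is not prognostic.

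**5. Stronger prognosis.** A two-eye model was also used, with contact lens acuity equal to BSCVA plus error and both eyes of BSCVA truncated at 0.04. By the formula in step 2, linear adjustment for the worse eye gains 1.9 to 2.2 points at a per-eye correlation of 0.5, 3.4 to 4.1 at 0.7, and 4.4 to 5.4 at 0.8. A two-eye simulation gave −0.3 to +3.0 points over correlations of 0 to 0.7. In a further simulation (4,000 trials, BSCVA area under the ROC curve 0.82, strata also prognostic), the linear model gained 3.3 points and a standardised logistic model 5.2. So +2 is not an upper bound.

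**6. Type I error at 82.5% v 92.5%.** Exact enumeration of the planned rule gives 0.0298 at 109 per group and 0.0285 at 122. In the 4,000-trial simulation, adjusted tests gave about 0.025 to 0.038 and the crude test 0.026 to 0.036. In the 20,000-trial stratified runs, the BSCVA-and-strata model with HC3 gave 0.024 to 0.030 and crude 0.025 to 0.032. HC3 by itself lowers error slightly, so that small difference is not evidence for adjustment.

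**The case against.** The strongest case against is that nothing here is wrong. The crude test is simple, prespecified and matched to the sample size; the gain rests on a prognostic strength that the documents do not give; and entry is cut at the endpoint's own threshold, which narrows the range of BSCVA. At modest prognosis the change is nil or slightly negative. Shifts of this size also arise from discreteness: exact power of the planned rule runs from 78.8% at 107 per arm to 81.9% at 112. All of this stands, and it is why the point is optional.

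Three stronger readings are tempting, and the documents support none of them.

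- **That the crude test is biased or invalid because it ignores BSCVA and the strata.** Assignment is randomised, so leaving them out does not bias the difference. The slight excess over 0.025 comes from the Wald method, and adjustment does not remove it.
- **That the planning rate shows BSCVA to be prognostic.** Quoting 92.5% for subjects at 0.04 or better matches the rate to the entry criterion. It says nothing about variation among eligible subjects.
- **That the plan contains no adjusted analysis.** The blacked-out text prevents that conclusion.

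**Conclusion.** An optional efficiency improvement, to be considered rather than required. The visible primary analysis is sound in large samples and agrees with its sample size, but leaves unused a baseline measurement already collected on the endpoint's scale. The power change depends on assumption: about −0.3 points if BSCVA is not prognostic (about −1 with HC3 and stratum terms), around zero at OR 1.5 to 2 per SD, and about +1 to +5 if strongly prognostic. The top of that range needs a per-eye correlation near 0.8, or a standardised logistic model with a very strong predictor. The case rests on BSCVA alone; adding ancestry and sphere sign brought no gain.

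**What to change.** In section 12.3.2, before unmasking, prespecify a risk difference adjusted for continuous screening BSCVA in the worse eye. Either a linear model for the binary outcome or a standardised logistic model keeps the scale of the margin. Use an HC1-type robust 95% interval, compare its lower limit with −10%, and report the crude Wald difference alongside. Use the screening value, because BSCVA at the dispensing visit is measured after assignment.

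Ancestry and sphere sign may be added to reflect the randomisation, but not in expectation of power. If sphere sign is included, fix a rule on the masked pooled count for very few plus-power subjects. Keep site terms out of the primary model: 13 × 2 × 2 = 52 cells hold about 218/52 = 4.2 evaluable subjects each, and only 218 × 0.075 ≈ 16 failures are expected in all.

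If the sponsor keeps the crude test as primary, prespecify the adjusted estimate as a sensitivity analysis, at no cost in power for the primary test.

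The cost is one paragraph and one model. Data collection, sample size, margin and alpha do not change. As a primary analysis it risks a few tenths of a point of power if BSCVA proves uninformative.
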